4.6. Safety Analyses

Safety analyses will be conducted using the SA Set.

4.6.1 Adverse Events

All AEs will be coded using the MedDRA coding system and displayed in tables by treatment received and in data listings using system organ class and preferred term. AE grade assessment will be based on investigator reporting using the National Cancer Institute Common Terminology Criteria for Adverse Events.

Analyses of AEs will focus on those events that are considered treatment-emergent, where treatment-emergent is defined as any AE with onset the day of or after the administration of study medication through the end of the study (28 days after last dose administered), or any event that was present at baseline but worsened in intensity or was subsequently considered drug-related by the Investigator through the end of the study.

The number and percentage of patients with any treatment-emergent adverse event (TEAE), with any TEAE assessed by the Investigator as related to treatment (definite, probable, or possible relationship), with any serious TEAE, with any related serious TEAE, with any TEAE leading to study drug withdrawal, or with any TEAE leading to death will be summarized.

In these tabulations, each patient will contribute only once (i.e., the most related occurrence

or the most intense occurrence) to each of the incidence rates in the descriptive analysis, regardless of the number of episodes.

All AEs occurring on-study will be listed in patient data listings. Listings will also be provided for the following: drug product related TEAEs, Serious TEAEs, drug product related serious TEAEs, TEAEs leading to study drug withdrawal, and deaths.

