#### **Duration of treatment:**

All patients receive study treatment for 16 weeks. Patients may elect to continue setmelanotide treatment by enrolling in an extension study (RM-493-022) immediately following the last dose in this study; if the extension study is not yet open at the current clinic site, patients may continue treatment in the current study for up to one year, resulting in treatment duration of up to 16 months.

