For pre-amendment 9 patients, the treatment phase of the study will begin with an initial period of dose titration in 0.5 mg increments and lasting between 2 and 12 weeks. The dosing will range from as brief as a single dose step at either 1.0 mg for adults or 0.5 mg for adolescent (ages 12 – 18 years) patients, to as many as 5 (adults) or 6 (adolescents) dose steps to reach 3.0 mg once-daily. The highest potential dose allowed in dose titration, however, is expected to be 2.5 mg, with the option to progress further to 3.0 mg if there is a lack of response at 2.5 mg. Thus, each patient will have his/her dose individualized depending on the number of dosing increments administered, where each individual patient's therapeutic dose will be established by upwards dose titration in 2-week intervals. Thereafter, patients will continue on active treatment at their optimal therapeutic dose for an additional 10 weeks, for a total combined dosing duration of 12 weeks at the individual patient's established therapeutic dose [i.e., the last 2 weeks during dose titration plus 10 weeks of open label treatment]. Patients will complete all procedures as described [Table 1-1](#), [Table 1-2](#), [Table 1-3](#). Patients who demonstrate at least 5 kg weight loss at the end of the Open Label Treatment Period (or 5% weight loss for patients with baseline body weight < 100 kg) will continue onto the long-term (1 year) extension period. It is planned that the individual patient's therapeutic dose, established during the initial period of dose titration, will continue throughout the study. In consenting patients, a 2- to 4-week period of active treatment withdrawal will be included during the 1-year extension.

Thus, pre-amendment patients will progress sequentially through the study as depicted in [Figure 1](#).

For post-amendment 9 patients, upon providing informed consent, patients will enter the Screening Period. During the Screening Period, patients will be assessed for eligibility and complete all screening procedures as described in [Table 2](#). Each patient's genetic information will be reviewed by the Sponsor to confirm the patient is eligible for the study. During the Screening Period, each patient will be instructed to complete a hunger questionnaire on a daily basis and will be required to have completed at least four days of the questionnaire prior to first dose.

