2. ANALYSIS POPULATION

2.1. Population Definitions

The following analysis populations will be evaluated and used for presentation and analysis of the data:

- Safety Analysis (SA) Set: All patients who received at least 1 dose of study drug, excluding patients from Axis Sites #22 through #27 inclusive.
- Full Analysis Set (FAS): All patients who received at least 1 dose of study drug and have baseline weight data, excluding patients from Axis Sites #22 through #27 inclusive.
- Completer's Set (CS): All patients in the FAS who have non-missing weight data collected at least once between 60 days and 120 days on therapeutic dose, inclusive.
 - For patients enrolled prior to amendment 9, therapeutic dose will be considered the maximum dose received during the dose escalation phase (identified by Clinical Visit 2X). For patients enrolled post-amendment 9, the therapeutic dose will be considered the dose received at Visit 3.
 - The first date that this dose was received will be considered the date of the first therapeutic dose (this will be the date of Visit 3 for post-amendment 9 patients). If a patient has a visit falling within 60 to 120 days after first therapeutic dose and was still on treatment, this visit should be considered for analysis as ~3 months of treatment. If a patient has two visits falling within this window, the visit closest to Day 90 in which the patient was still on treatment should be considered. If a patient has two visits falling within this window that are equidistant from Day 90, the later visit should be considered. For post-amendment 9 patients, if the patient's last visit during the study is Study Visit 5 and the patient is still on treatment, then that date should be used for this analysis, even if it does not fall within 60 to 120 days after first therapeutic dose. If a patient has no visit falling within this window, this patient will be treated as missing for completer's analysis purposes. If a patient has no visit falling within this window and no observation prior to the window, this patient will be treated as missing for analysis purposes, as well.
- Per-Protocol (PP) Set: All patients in the FAS without any major protocol violations.

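### Whole-study TEAE percentages partly reflect time in study, because planned dosing ranges from 12 to at most 74 weeks and SAP 4.6.1 sets no common window or time-at-risk denominator

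*SAP*

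**What the plan says.** SAP 4.6.1 (Adverse Events) gives the statistic as "The number and percentage of patients with any treatment-emergent adverse event (TEAE), with any TEAE assessed by the Investigator as related to treatment", followed by serious events, events leading to withdrawal and deaths. The window runs from first dose "through the end of the study (28 days after last dose administered". Each patient contributes once "to each of the incidence rates in the descriptive analysis, regardless of the number of episodes". The denominator is the Safety Analysis Set of SAP 2.1, "All patients who received at least 1 dose of study drug, excluding patients from Axis Sites #22 through #27 inclusive", so patients from both study designs are together.

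Planned treatment time comes from three places:

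- **Before Amendment 9** (SAP 1.3.1): an "initial period of dose titration in 0.5 mg increments and lasting between 2 and 12 weeks", after which "patients will continue on active treatment at their optimal therapeutic dose for an additional 10 weeks". Patients who lost at least 5 kg, or 5% if they weighed under 100 kg at baseline, "will continue onto the long-term (1 year) extension period". SAP Table 1-3 gives that extension as 52 weeks.
- **Current design** (Protocol synopsis, Duration of treatment): 16 weeks, then the separate extension study. Where that study is not yet open at the site, "patients may continue treatment in the current study for up to one year, resulting in treatment duration of up to 16 months".
- **Transition** (SAP 1.3.1): earlier patients move in time to the Amendment 9 schedule.

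SAP 1.3.5 lists safety and tolerability first among the secondary endpoints. SAP 3.8 says that primary, secondary and exploratory endpoints will be looked at separately in each genetic subgroup. Protocol 8.1 expects 1 to 15 patients per subgroup.

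**The concern.** A percentage of patients with at least one event rises with the time over which events can be seen. When that time differs several-fold by design, two groups with the same underlying risk can show different percentages. The visible text of SAP 4.6.1 has no common cut-off, no person-time denominator, and no separation of the core period from the extension or bridging period.

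The reading at stake is the one by subgroup. Protocol 7.3 says the study is to evaluate safety and tolerability in each population and inform whether to develop further there. In a cohort of a few patients, one or two long-treated members can move the figure noticeably. For patients enrolled before Amendment 9 there is a second link: extra time was given only to those who lost weight, so exposure and response are tied in that era.

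**Working it through.** **1. The plan's own durations.** The current design gives 16 + 52 = 68 weeks, or 68 × 7 / 30.44 = 15.6 months, which agrees with the stated maximum of 16 months. In SAP Table 1-3 the calendar restarts at the therapeutic dose, so the last extension visit falls at 12 + 52 = 64 weeks, and 64 × 7 + 1 = Day 449, as printed. Adolescent titration from 0.5 to 3.0 mg in 0.5 mg steps is 6 steps of 2 weeks, or 12 weeks, matching the stated upper limit.

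**2. Planned dosing and event window.** The window adds 4 weeks (28 days).

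| Group | Dosing (weeks) | Window with full tail (weeks) |
|---|---|---|
| Pre-Amendment 9, threshold not met | 2 + 10 = 12 to 12 + 10 = 22 | 16 to 26 |
| Pre-Amendment 9, threshold met | 12 + 52 = 64 to 22 + 52 = 74 | 68 to 78 |
| Current, no bridging | 16 | 20 |
| Current, maximum bridging | 68 | 72 |

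Dosing spans a ratio of 74/12 = 6.2, and the window 78/16 = 4.9. The two pre-Amendment 9 rows do not overlap. Patients who stop early fall below these figures, and those rolling straight into the extension study may not have the 4-week tail here.

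**3. Effect on the crude percentage.** The documents give no adverse event rates (Protocol 12.2.2 refers to the Investigator Brochure), so the hazard h per year is an assumption. For a constant hazard and t weeks at risk, the crude percentage is 1 − exp(−h × t/52). The comparison within the current design is 20 against 72 weeks:

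| h per year | 20 weeks | 72 weeks | Ratio |
|---|---|---|---|
| 0.2 | 7.4% | 24.2% | 3.3 |
| 0.5 | 17.5% | 50.0% | 2.9 |
| 2 | 53.7% | 93.7% | 1.7 |
| 5 | 85.4% | 99.9% | 1.2 |

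For h = 0.5: 1 − exp(−0.5 × 20/52) = 1 − exp(−0.192) = 0.175, and 1 − exp(−0.5 × 72/52) = 1 − exp(−0.692) = 0.500.

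**4. Falling hazard.** Take a Weibull shape of 0.5 and let p be the assumed proportion of patients with the event by week 12. The crude percentage is 1 − exp(ln(1 − p) × (t/12)^0.5). With p = 5%, it is 6.4% at 20 weeks and 11.8% at 72 (ratio 1.8). With p = 20%, it is 25.0% and 42.1% (1.7). With p = 50%, it is 59.1% and 81.7% (1.4). If all onsets fall in the first weeks, the two percentages are equal.

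**5. What a person-time denominator does.** At h = 0.5, a cohort followed entirely for 20 weeks shows 17.5%, one split evenly between 20 and 72 weeks shows (17.5 + 50.0)/2 = 33.7%, and one followed entirely for 72 weeks shows 50.0%. Expected time at risk to first event is (1 − exp(−h × t/52))/h, so patients with an event per patient-year equals 0.5 in all three.

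**The case against.** Several points on the other side stand and limit the concern.

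- **Single-arm and descriptive.** No treatment contrast is biased. SAP 4.6.1 describes its tables by treatment received, and no table by era or by responder status appears. But SAP 3.8 covers secondary endpoints by subgroup and SAP 1.3.5 makes safety one of them, so comparison between subgroups is invited.
- **Extremes are rare.** Reaching 74 weeks needs the full six-step adolescent titration, although SAP 1.3.1 expects titration to go no higher than 2.5 mg. Earlier patients also transition to the new schedule or may roll over to the extension study. That is why the main illustration above uses the current design.
- **Partly handled elsewhere.** Events of special interest, injection-site findings, laboratory values and vital signs are summarized by visit, and all adverse events are listed by patient. The TEAE tables themselves are not helped by this.
- **Redaction.** Contents entries between SAP 4.6.6 and 4.6.9 are hidden. An exposure table may exist there, so its absence can be stated only for the visible text.
- **Limits of exposure-adjusted rates.** If events cluster early, dividing by long follow-up makes long-treated patients look safer than they are. Such rates therefore belong beside a common-window table and cannot replace it.

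Two stronger readings are tempting. A reader might infer that responders are followed longer throughout the study. The documents support this as a rule only before Amendment 9, and they do not give the numbers enrolled before and after. A reader might also infer that the percentages measure time in study as much as drug risk. Without event rates that cannot be shown, and for early-onset or very common events the effect is small.

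**Conclusion.** The point holds in a limited form and is worth acting on. Whole-study TEAE percentages in SAP 4.6.1 partly reflect length of follow-up, which differs by design from about 16 to at most 78 weeks. The link between exposure and response is confined to patients enrolled before Amendment 9.

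The size is uncertain. Within the current design it is 2.9-fold at an assumed constant hazard of 0.5 per year and somewhat more at lower hazards. It falls to about 2 or less when the hazard is high or declines over time, and to near 1 for events that start in the first weeks. Less common events with later onset, which may include serious events or events leading to withdrawal, would be the most affected. These ratios assume the planned durations with the full 28-day tail. Actual exposure will depend on bridging, rollover and withdrawal, none of which the documents quantify. It is a reporting improvement for an exploratory study and does not threaten the primary endpoint.

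**What to change.** In SAP 4.6.1:

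1. Add TEAE tables restricted to onset in the first 16 weeks from first dose, shown apart from the extension or bridging period. The 28-day tail brings even planned 12-week dosing to 16 weeks of observation. This equalizes planned observation time, not dosing time, and patients who leave early still contribute less.
2. Beside each whole-study crude percentage, give patients with an event per patient-year at risk, with time counted to first event. State that the rate assumes a roughly constant hazard and is imprecise in small cohorts.
3. Report extent of exposure (days on drug and patient-years) by genetic subgroup and by pre- or post-Amendment 9 enrollment, if the redacted sections do not already do so.

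The cost is SAP wording and a few tables. Onset dates (Protocol 13.4) and the daily dosing log (Protocol 9.6) are already collected, and trial conduct does not change. The price in interpretation is that rates in cohorts of 1 to 15 patients will be very imprecise.

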4.6.1 Events of Special Interest

Events of special interest include recognized events within the categories of skin hyperpigmentation and sexual events (male or female). The number and percentage of subjects with events of special interest will be summarized by visit.

In these tabulations, each subject will contribute only once per visit to each of the incidence rates in the descriptive analysis, regardless of the number of episodes.

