#### 13.4. Statistical Methods

Statistical methods, populations, and approaches to missing data will be outlined in the SAP.

The primary endpoint is defined as the proportion of patients in each subgroup of RGDO who achieve at least 5% body weight reduction from baseline, at ~3 months of treatment with setmelanotide. Summary of the primary endpoints and the associated Clopper-Pearson confidence interval will be provided.

The comparison of post-treatment values versus baseline will be carried out via 1-sided statistical test at an alpha=0.05. No adjustment for multiplicity is needed for the single primary endpoint; weight change after 1 year of treatment in subjects who continue in the study past 3 months will also be analyzed without adjustment for multiplicity. In addition, no adjustment for multiplicity will be included for the many rare genetic obesity populations in this study as these different populations are included in this study only for administrative convenience. All the p-values and/or confidence intervals should be considered exploratory.

For the primary endpoint, and all other endpoints, the last value obtained prior to the first dose of active treatment will be considered the baseline value for statistical analyses.

As this patient population is extremely rare, efforts will be made to keep all patients in the study, and all data collected, even if outside of visit windows, will be included in all analyses of endpoints.

AEs will be coded by using the most current version of Medical Dictionary for Regulatory Activities (MedDRA) and summarized by system organ class, preferred term, and treatment group for the number and percent of AEs reported, the number of patients reporting each AE, and the number of patients with any AE.

A by-patient AE data listing including onset and resolution dates, verbatim term, preferred term, treatment, severity, relationship to treatment, action taken, and outcome will be provided.

Safety data including laboratory evaluations and vital signs assessments will be summarized by time of collection and by treatment group. In addition, change from baseline to any post-dose values will be summarized for vital signs and clinical laboratory results. Frequency of patients with abnormal safety laboratory results will be tabulated by treatment.

Plasma concentrations of setmelanotide will be summarized. Plasma concentrations may be compared to pharmacodynamic endpoints.

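### The events-of-special-interest table counts patients once per visit, so no planned table shows how many patients ever have an event in either pooled category

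*SAP*

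**What the plan says.** SAP 4.6.1 (Events of Special Interest) names two categories, skin hyperpigmentation and sexual events in either sex. It specifies one display: "The number and percentage of subjects with events of special interest will be summarized by visit". The counting rule is that "each subject will contribute only once per visit to each of the incidence rates in the descriptive analysis", however many episodes occur. The section does not say whether a visit cell holds new onsets or events still ongoing, or what the denominator is. It gives no list of preferred terms for either category.

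The preceding section, SAP 4.6.1 (Adverse Events), treats adverse events in general differently. They are "displayed in tables by treatment received and in data listings using system organ class and preferred term", and the counting rule there has no visit qualifier: "In these tabulations, each patient will contribute only once (i.e., the most related occurrence", or the most intense one. The treatment-emergent period runs from the first administration to 28 days after the last dose. Protocol 13.4 likewise plans, by system organ class and preferred term, "the number of patients reporting each AE, and the number of patients with any AE". For individual records, SAP 4.6.1 adds: "All AEs occurring on-study will be listed in patient data listings". Protocol 13.4 puts onset and resolution dates in the by-patient listing.

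**The concern.** The first question about a safety category chosen for special attention is what fraction of patients get it, and how soon. A once-per-visit count does not answer that, although the SAP calls its cells incidence rates. Visit cells cannot be summed, because the same patient may count at several visits, and no single cell is defined so that it equals the share ever affected. The two singled-out categories therefore get a less interpretable summary than ordinary treatment-emergent events.

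The visit axis adds a second difficulty. Under SAP 1.3.1, patients enrolled before amendment 9 titrate for 2 to 12 weeks and then have 10 more weeks to their V6, so that visit falls 2 + 10 = 12 to 12 + 10 = 22 weeks after first dose. For patients enrolled from amendment 9 onward, V6 is at week 16. SAP 3.11 leaves visit mapping for some of the earlier patients to a separate document. A visit cell can thus mix different exposure times.

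The frequency of adverse events is a named secondary endpoint (Protocol 6.2, SAP 1.3.5), and SAP 3.12 foresees data cuts in support of a regulatory submission. A table that is easy to misread as incidence is worth correcting.

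**Working it through.** The documents give no rate for these events, so there is no stated figure to reproduce. All event counts below are assumptions. The subgroup size N = 15 is the top of the 1-15 range in Protocol 8.1. The five visits are V3 to V7 of the current schedule.

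**Step 1: can the preferred-term rows supply the category figure?** Suppose a category has two preferred terms, reported by 4 and 5 of 15 patients.

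- Full overlap: max(4, 5)/15 = 5/15 = 33.3%.
- No overlap: (4 + 5)/15 = 9/15 = 60.0%.

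The rows leave the category share anywhere between these limits.

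**Step 2: can the by-visit cells supply it?** Suppose 9 of 15 patients are ever affected, so the share ever affected is 60.0%.

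| Reading of the by-visit cell | Calculation | Cells, V3 to V7 | Against 60.0% |
|---|---|---|---|
| A. New onsets, spread evenly, fixed N | 9/5/15 | about 12.0% each | below |
| B. Lasting events counted while ongoing, onsets spread evenly, fixed N | 9 × (k/5)/15, k = 1 to 5 | 12.0, 24.0, 36.0, 48.0, 60.0% | below, then equal at the last visit |
| C. Lasting events counted while ongoing, all onsets by V3, fixed N | 9/15 | 60.0% each | equal |
| D. As C, but patients attending as denominator; 1 or 3 unaffected patients have left | 9/14 or 9/12 | 64.3% or 75.0% once they have left | above |

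**Step 3: range.** With 3 to 12 of 15 ever affected (20% to 80%), reading A gives 3/5/15 = 4.0% to 12/5/15 = 16.0% per cell. Reading D with three unaffected dropouts gives 3/12 = 25.0% to 12/12 = 100.0%.

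A by-visit count can never exceed the count ever affected, but a by-visit percentage can. The SAP text allows all four readings.

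**The case against.** The strongest reply is that the information is not lost. The share of patients who ever report each preferred term is planned, every on-study event is listed by patient, and the listing carries dates. With subgroups of 1 to 15 patients, anyone could count the category by hand. Adverse events are assessed at every visit, so a by-visit display is workable and does say something about timing. Nothing in the documents makes an endpoint, an eligibility decision or a stopping rule depend on this table. All of that stands, and it limits the severity. It does not supply a planned category figure: a count made from listings would be unplanned and would rest on terms chosen after the data are seen, in an open-label study.

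Two stronger readings are tempting, and the documents do not support either.

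- A reader might infer that the frequency of these events is never reported. The preferred-term tables and the listings contradict that. What is missing is the pooled category figure.
- A reader might infer that every visit cell understates the risk. Suppose 15% of unaffected patients have onset in each four-week interval. Onset cells at V3 to V6 are then 0.15, 0.85 × 0.15, 0.85² × 0.15 and 0.85³ × 0.15, or 15, 13, 11 and 9%, against 1 − 0.85⁴ = 48% affected by V6. If the events last and are counted while ongoing with no dropout, the same rate gives 15, 28, 39 and 48%, and the V6 cell equals the cumulative share. The 48% contrast therefore rests on one assumed rate under one reading that the SAP does not specify.

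**Conclusion.** The point holds as a minor gap in specification. In the readable text, the special-interest events are tabulated only by visit with a once-per-visit rule, and no planned table gives the number and percentage of patients ever affected in each pooled category. Preferred-term rows bound that figure but do not determine it (33.3% to 60.0% in the assumed example). By-visit cells may lie below, at or above it, because the onset or ongoing rule and the denominator are unstated. The size of any discrepancy cannot be predicted, since the documents give no event rate; the figures above show direction and range only. The conclusion rests on the general adverse event rule being applied once per patient to each preferred term, which is its natural reading, and on no redacted part of the SAP adding such a table.

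**What to change.** In SAP 4.6.1 (Events of Special Interest), add a table giving, separately for skin hyperpigmentation and sexual events, the number and percentage of Safety Analysis Set patients with at least one event. Count each patient once over the treatment-emergent period that SAP 4.6.1 (Adverse Events) already defines. Show it by genetic subgroup and overall, with day of first onset measured from first dose. That period is preferable to a cut at V6, which falls at different exposure times before and after amendment 9. Name the preferred terms that make up each category so that the row can be programmed before the data are reviewed.

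Keep the by-visit display as supportive, relabel it as prevalence of ongoing events, and state its denominator.

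The cost is one extra table from dates already collected, with no change to design or data collection. The headline percentage may be higher than individual visit cells.
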